The nonclinical toxicity profile was used to determine the starting dose and develop appropriate exclusion criteria and safety monitoring for this study. In addition, frequent complete blood counts (CBCs) and chemistry (including liver function) tests will be performed to assess the potential nonantigen dependent myelosuppression and liver function effects of BMS-986148. Subjects will be evaluated frequently by physical examination (PE), and they will be assessed for the development of ocular symptoms and peripheral neuropathy (although not seen in toxicology studies, peripheral neuropathy is a known side effect of some microtubule inhibitors). Subjects with Grade 2 or higher ocular symptoms or peripheral neuropathy will be excluded from the study. Ophthalmological examination by an ophthalmologist or locally qualified personnel will include an 8-point exam (visual acuity, pupils, extraocular motility and alignment, tonometry, visual field, external examination, slit lamp examination, and fundoscopy) at baseline and focused exams with visual acuity, slit lamp, and as indicated will be conducted during the study. Safety assessments are outlined in [Section 5.3](#). The dose escalation plan uses Grade 2 ocular symptoms, as well as other Grade 3 and 4 DLTs, to trigger a transition from 100% dose escalation increments to a dose escalation increment sequence of 67%, 50%, 40%, and

continuing at 33%, to reduce the risk of drug related AEs. No significant ocular toxicities have been observed in the 30 subjects dosed as of 01 July 2016.

In addition, subjects with a left ventricular ejection fraction (LVEF) below the lower limit of normal, New York Heart Association (NYHA) Class 2 or higher heart failure, and elevated Troponin I or T will be excluded from the study. Cardiac monitoring with echocardiogram, EKG, and Troponin T or I will be conducted during the study. Safety assessments are outlined in [Section 5.3](#). As of 01 July 2016, no troponin elevations were noted in the 30 subjects dosed in the monotherapy escalation of Part 1A. One SAE of Grade 3 pericardial effusion related to study drug was observed after the second cycle of BMS-986148 at the high dose of 1.6 mg/kg Q3W in Part 1A. This dose has been determined to be above the MTD, and no additional subjects will be treated at this dose level.

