Procedure a	Pre-Screening	Screening Visit D-28 to D-1	C1D1	C1D2	C1D4 b	C1D8	C1D15	Notes
Targeted PE						X	X	To include signs and symptoms of peripheral neuropathy and ocular toxicity. Any grade ocular toxicity requires ophthalmologist consultation and discussion with medical monitor as appropriate.
Ophthalmological Examination c		X						Performed by ophthalmologist or locally qualified personnel. Any abnormality must be discussed with the medical monitor prior to dosing.
Physical Measurements		X	X					Height (screening only), weight.
Vital Signs d		X	X			X	X	Body temperature, blood pressure, and heart rate. Blood pressure and heart rate should be measured after the subject has been resting quietly for at least 5 minutes.
ECGs		X	X	X		X		ECGs should be recorded after the subject has been supine for at least 5 minutes. Triplicate ECGs should be taken within 5 minutes of the previous measurement. For ALL subjects in Part 1 and up to 20 subjects in Part 2: time matched for PK; triplicate evaluations at C1D1 pre-dose and EOI, C1D2 (24 hours post dose), and C1D8 (168 hours post dose) AND at C4D1 pre-dose and EOI, C4D2 (24 hours post dose), and C4D8 (168 hours post dose). QTcF assessment > 450 msec must be confirmed on repeat ECG.
MUGA/Echocardiogram		X						MUGA or echocardiogram done at screening to document LVEF. Echocardiogram done at the start of Cycle 3, then every 3 cycles thereafter, and as clinically indicated for the evaluation of pericardial

**Table 5.1-2: Screening and Cycle 1, Parts 1A and 2 (Q3W BMS-986148 Monotherapy Dosing / 21 Day Cycle) Procedural Outline (CA008002)**

Procedure a	Pre-Screening	Screening Visit D-28 to D-1	C1D1	C1D2	C1D4 b	C1D8	C1D15	Notes
								effusion.
Laboratory Tests		X	X	X	X	X	X	If the screening laboratory tests are performed within 24 hours prior to dosing on Day 1, then a single exam may count as both the screening and pre-dose evaluation. See Section 5.3.1 Urine - screening only, unless clinically indicated. C1D4 and C4D4: CBC only.
Troponin T or I		X	X			X	X	During Part 1 only. The same evaluation must be collected throughout the study.
Pregnancy Test		X	X					
PK and Immunogenicity Assessments (See Section 5.5)								
Biomarker Assessments [REDACTED]								
[REDACTED]								

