**Table 5.1-7: Cycle 2 to Off Study Visit (Part 3: Nivolumab Combination Arm / 21 Day Cycle) Procedural Outline (CA008002)**

Procedure a	C2 and C3			C4					C5 and Beyond	EOT	Follow-up (30, 60, and 100 Days after Last Dose)	Survival Follow-up b	Notes
	D1	D 8	D1 5	D1	D2	D4 c	D8	D15	D1		(±5 days)	(±2 weeks)	
Ophthalmological Examination d	Start of Cycle 2, every 2 cycles thereafter and as clinically indicated									X			Performed by ophthalmologist or locally qualified personnel. Any abnormality must be discussed with the medical monitor prior to dosing. Ophthalmological exams can be done up to 72 hours prior to dosing.
Physical Measurements	X			X					X	X	X		Weight only.
Vital Signs e	X	X	X	X					X	X	X		See note in screening procedures.
ECGs	X			X	X		X		X	X	X		See note in screening procedures.
Echocardiogram	X			See notes						X			Echocardiogram done at the start of Cycle 2 and Cycle 3, then every 3 cycles thereafter, and as clinically indicated for the evaluation of pericardial effusion. On treatment echocardiogram exams may be done up to 72 hours prior to dosing.
Laboratory Tests	X	X	X	X		X			X	X	X		See note in screening procedures and Section 5.3.1 .

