**Table 5.1-8: Retreatment Day 0 and Cycle 1 Onwards (Part 3 Retreatment): Nivolumab Combination Arm / 21 Day Cycle) Procedural Outline (CA008002)**

Procedure a	Day 0	C1 and Beyond D1	EOT	Follow-up (30, 60, and 100 Days after Last Dose) (±5 days)	Survival Follow-up b (±2 weeks)	Notes
						cycles thereafter and as clinically indicated.
Physical Measurements	X	X	X	X		Height (screening only), weight.
Vital Signs d	X	X	X	X		Body temperature, blood pressure, and heart rate. Blood pressure and heart rate should be measured after the subject has been resting quietly for at least 5 minutes.
Oxygen Saturation	X					Pulse oximetry collected at rest at Day 0 and as clinically indicated on study.
ECGs	X	X	X	X		ECGs should be recorded after the subject has been supine for at least 5 minutes.
MUGA/Echocardiogram	X	See notes	X			MUGA or echocardiogram done at Day 0 to document LVEF. Echocardiogram done at the start of Cycle 2 and Cycle 3, then every 3 cycles thereafter, and as clinically indicated for the evaluation of pericardial effusion
Laboratory Tests	X	X	X	X		If the Day 0 laboratory tests are performed within 24 hours prior to dosing on Day 1 then a single exam may count as both the screening and pre-dose evaluation. Repeat the following if >6 months since last treatment: Hep B surface antigen and Hep C antibody (if Hep C antibody is positive reflex to Hep C RNA) or Hep C RNA will be done at screening. Note: Testing for HIV-1 and HIV-2 must be performed at sites where mandated by local

**Table 5.1-8: Retreatment Day 0 and Cycle 1 Onwards (Part 3 Retreatment): Nivolumab Combination Arm / 21 Day Cycle) Procedural Outline (CA008002)**

Procedure a	Day 0	C1 and Beyond D1	EOT	Follow-up (30, 60, and 100 Days after Last Dose) (±5 days)	Survival Follow-up b (±2 weeks)	Notes
						requirements See Section 5.3.1 Urine - Day 0 only, unless clinically indicated.
Thyroid Function	X	X				TSH with reflexive fT3 and fT4 to be done every 6 weeks.
Pregnancy Test	X	X	X	X		

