Cardiac monitoring with echocardiogram at baseline, start of Cycle 3, then every 3 cycles, and EOT will be conducted during the Part 1 and 2 (Monotherapy treatment) . For subject in Part 3 combination treatment, an additional echocardiogram at the start of cycle 2 will be done. MUGA scan can be used for the assessment of LVEF at baseline. Echocardiograms done during treatment for the monitoring of pericardial effusion may be obtained more frequently if indicated. Troponin T or I will be monitored QW during the first cycle. Grade 1 elevation requires dose interruption of study drug and repeat assessment within 72 hours; BMS-986148 should be discontinued if Grade 1 Troponin T or I is confirmed when repeated assessment occurs. If persistent elevation, dose discontinuation should be considered at the discretion of the consulting cardiologist and discussion with the medical monitor. Grade 3 elevation of Troponin I or T requires discontinuation of study drug and prompt consultation and management with a cardiologist is recommended until it resolves.

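### MUGA alone is accepted as the screening cardiac test, so a subject can be dosed without a baseline echocardiogram for the pericardial effusion that later echocardiograms monitor

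*Protocol*

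**What the plan says.** **Screening.** Table 5.1-2 (Parts 1A and 2, Q3W) reads "MUGA or echocardiogram done at screening to document LVEF". Tables 5.1-4 (QW) and 5.1-6 (Part 3) use the same wording. For Part 3 retreatment, Table 5.1-8 has "MUGA or echocardiogram done at Day 0 to document LVEF". The matching exclusion criterion in Section 3.3.2 concerns LVEF only and accepts either test. No eligibility criterion mentions pericardial effusion.

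**On treatment.** Only echocardiograms are scheduled. Table 5.1-2 notes "Echocardiogram done at the start of Cycle 3, then every 3 cycles thereafter, and as clinically indicated for the evaluation of pericardial" effusion. Part 3 starts one cycle sooner (Table 5.1-7): "Echocardiogram done at the start of Cycle 2 and Cycle 3, then every 3 cycles thereafter".

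**Section 5.3.** One paragraph contains three relevant statements:
- for Parts 1 and 2, "Cardiac monitoring with echocardiogram at baseline, start of Cycle 3, then every 3 cycles, and EOT will be conducted"
- then, "MUGA scan can be used for the assessment of LVEF at baseline"
- then, "Echocardiograms done during treatment for the monitoring of pericardial effusion may be obtained more frequently if indicated"

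**Known event.** Section 1.5.1 reports: "One SAE of Grade 3 pericardial effusion related to study drug was observed after the second cycle of BMS-986148". The dose was 1.6 mg/kg Q3W, which the same section places above the MTD and closes to further subjects.

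**The concern.** The screening test is chosen to answer one question (ejection fraction), and the on-treatment test is used for another (effusion). A subject who has only MUGA at screening meets the second question for the first time after dosing.

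This matters because Section 6 defines an adverse event as something new or a worsening of something already present, and the primary endpoint in Section 8.3.1 counts such events at worst grade. Deciding whether an effusion is new, worse or unchanged needs a baseline. Section 1.5.1 names serosal surfaces of thoracic and abdominal organs among the main antigen-dependent toxicity targets in animals, and one drug-related serious effusion has already occurred. Some subjects may also arrive with an effusion: NSCLC and pleural mesothelioma are eligible, and Appendix 4 lists pericardial effusion among non-measurable lesions.

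Elsewhere the protocol keeps baseline and follow-up on the same test. The troponin type must not change during the study (Table 5.1-2), and tumour lesions must be followed by the method used at baseline (Appendix 4, Section 1.4.2). Effusion monitoring lacks that protection.

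**Working it through.** The plan gives no figure to reproduce. The check compares the texts and counts days from the stated cycle lengths.

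**1. Is a baseline echocardiogram required?**

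| Source | Baseline test | Stated purpose |
|---|---|---|
| Tables 5.1-2, 5.1-4, 5.1-6 | MUGA or echocardiogram | LVEF |
| Table 5.1-8, Day 0 | MUGA or echocardiogram | LVEF |
| Section 5.3, first statement | Echocardiogram (Parts 1 and 2) | Cardiac monitoring |
| Section 5.3, second statement | MUGA may be used | LVEF |

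The tables do not require one. Section 5.3 can be read as requiring one, with MUGA as an extra, or as letting MUGA take its place. A site that follows its table and performs MUGA alone complies with that table.

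**2. When is the first scheduled echocardiogram for that subject?**

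Start of Cycle k = Day (k − 1) × cycle length + 1, assuming no dose delay.

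- Q3W monotherapy: 21-day cycle, first echocardiogram at Cycle 3. (3 − 1) × 21 + 1 = Day 43. Doses on Days 1 and 22, so **2 doses**.
- QW: 28-day cycle with doses on Days 1, 8 and 15, first echocardiogram at Cycle 3. (3 − 1) × 28 + 1 = Day 57. 2 cycles × 3 = **6 doses**.
- Part 3: 21-day cycle, first echocardiogram at Cycle 2. (2 − 1) × 21 + 1 = Day 22, after **1 dose** of the combination.

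Tables 5.1-3, 5.1-5 and 5.1-7 allow the examination up to 72 hours before dosing, so the earliest days are 40, 54 and 19. The dose counts do not change.

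**3. How does this relate to the known event?** It was seen after the second cycle in the Q3W schedule. The Day 43 echocardiogram also follows two cycles, so in Q3W monotherapy the first scheduled look comes at about the stage where the event appeared.

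**4. How many subjects are affected?** This cannot be calculated. The documents give neither the share screened by MUGA nor the prevalence of effusion at baseline.

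**The case against.** **Section 5.3 already names a baseline echocardiogram, and MUGA there serves only LVEF.** This is the strongest reply. Its wording about an additional Cycle 2 echocardiogram in Part 3 also suggests the same base schedule there. The reply reduces the matter to a conflict between text and tables, but it does not remove the gap, because the tables accept MUGA alone.

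**Chest CT gives a like-for-like comparison.** This largely stands. Baseline chest CT falls within about 30 days of first dose and is repeated at the start of Cycle 3, within a week of the first monotherapy echocardiogram. In Part 3 the repeat comes one cycle after the Cycle 2 echocardiogram. Disease-related effusion would also be recorded at baseline as a non-target lesion (Appendix 4, Section 2.2). A reader might infer that effusions in MUGA-screened subjects are unclassifiable; that goes too far. However, the CT has no instruction to report effusion, and an effusion not judged to be disease need not be recorded as a lesion.

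**The table wording may tie effusion only to clinically indicated examinations.** That reading is possible for the tables, but the last Section 5.3 statement quoted above links on-treatment echocardiograms generally to effusion.

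Other inferences the documents do not support:
- *Distorted DLT attribution.* The first monotherapy echocardiograms (Days 43 and 57) fall well outside the 21- and 28-day windows. The Part 3 one sits at the edge of its window, but a nonhematologic DLT other than the listed eye events must be Grade 3 or higher.
- *LVEF compared across two modalities.* No on-treatment LVEF analysis appears in the protocol endpoints or in SAP Section 7.6.
- *Amendment 06 as a response to this gap.* The document history gives no reason for the added echocardiogram.
- *A rate of affected subjects.* Any figure would need assumed shares, and a count of small effusions is not comparable with one Grade 3 SAE.
- *Baseline effusion expected in every cohort.* Pancreatic, ovarian and gastric cancers are three of the five tumour types and are not thoracic.

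**Conclusion.** The point holds as a limited gap. The tables permit dosing without an echocardiographic baseline, Section 5.3 points the other way without settling it, and the monitored condition has produced one drug-related serious event. For a MUGA-screened subject, the first scheduled echocardiogram comes after 2, 6 or 1 doses, depending on the schedule.

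Its practical size is probably modest. CT and lesion recording cover part of the need, and the signal is a single SAE at a dose no longer used. The conclusion assumes that some sites use MUGA alone, which the tables allow but the documents do not quantify; if none do, nothing is lost. It is still worth correcting, because a pre-dose baseline cannot be obtained after dosing and the primary endpoint depends on what is new or worse. The need is weaker at retreatment, since those subjects have echocardiograms scheduled during and at the end of initial treatment. Even so, Section 3.1.7 allows progression up to 12 months after the last dose.

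**What to change.** Reconcile Tables 5.1-2, 5.1-4 and 5.1-6 with Section 5.3:
- Require a pre-dose echocardiogram at screening in all parts, recording the presence and size of any pericardial effusion, and LVEF.
- Allow MUGA at most as an optional addition for LVEF, not as a substitute.
- Apply the same rule at Day 0 in Table 5.1-8, as a lower priority.
- State in Section 5.3 that on-treatment effusions are assessed against that baseline.

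The LVEF exclusion criterion in Section 3.3.2 need not change.

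The cost is small. For sites now using MUGA, an echocardiogram replaces it, and every site already needs echocardiography on treatment. The downside is that sites lose the option of screening with MUGA alone.

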## **3.3 Study Population**

For entry into the study, the subject MUST fulfill the required eligibility criteria prior to dosing on Day 1. No exceptions will be granted.

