#### **2) Medical History and Concurrent Diseases**

- a) A serious, uncontrolled medical disorder which would impair the ability of the subject to receive protocol therapy
- b) Evidence of uncontrolled, active infection, requiring parenteral anti-bacterial, anti-viral, or anti-fungal therapy  $\leq 7$  days prior to administration of study medication
- c) Any major surgery within 4 weeks of study drug administration.
- d) Subjects with concomitant second malignancies (except adequately treated nonmelanomatous skin cancers or in situ bladder, breast, or cervical cancers) are excluded unless a complete remission was achieved at least 3 years prior to study entry and no additional therapy is required or anticipated to be required during the study period

- e) Uncontrolled or significant cardiovascular disease including:
  - i) Congestive heart failure NYHA Class 2 or greater within 3 months ([Appendix 6](#))
  - ii) LVEF < the institutional lower limit of normal as determined by MUGA or echocardiogram
  - iii) Active coronary artery disease, unstable or newly diagnosed angina, or myocardial infarction in the past 6 months
  - iv) History of congenital long QT syndrome or clinically significant ventricular arrhythmias (such as ventricular tachycardia, ventricular fibrillation, or Torsade de Pointes). Controlled atrial fibrillation is not an exclusion criterion.
  - v) Troponin (T or I) > the institutional upper limit of normal (ULN)
  - vi) History of myocarditis of any etiology
- f) NCI CTCAE v4.03 Grade 2 or higher peripheral neuropathy (sensory or motor)
- g) Grade 2 or higher eye disorders (inclusive of all NCI CTCAE v4.03 criteria). Mild eye symptoms such as blurry vision, either age-related or due to ocular or systemic disorder (eg, diabetes, dry eyes, cataracts, uncorrected refraction abnormality) may be allowed at the discretion of the ophthalmologist if deemed as not constituting a predisposition to drug-induced corneal deposits and blurry vision.
- h) Any other sound medical, psychiatric, and/or social reason as determined by the investigator
- i) **For Part 3 only** : Active, known, or suspected autoimmune disease
  - Participants with well-controlled asthma and/or mild allergic rhinitis (seasonal allergies) are eligible
  - Participants with the following disease conditions are also eligible:
    - Vitiligo
    - Type 1 diabetes mellitus
    - Residual hypothyroidism due to autoimmune condition only requiring hormone replacement

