Troponin I or T		X	X			X	X	X	For Part 1 only. The same evaluation must be collected throughout the study.
Pregnancy Test		X	X			X	X		
PK and Immunogenicity Assessments (See Section 5.5)									
Biomarker Assessments [REDACTED]									
[REDACTED]									
Tumor Sample (or Archival) Part 2: Required for Eligibility	X								For Part 2, subjects must have tumor mesothelin expression [REDACTED] No other protocol-specific eligibility procedures/assessment should be conducted until the tumor mesothelin expression is confirmed. Tumor material from archived samples will be used for the IHC analyses. If archived tumor material is unavailable or unsuitable for evaluation, then tumor material from a fresh biopsy must be provided for these analyses. If archived tumor material is to be used, then a tumor paraffin block or unstained slides from a tumor tissue

**Table 5.1-4: Screening and Cycle 1, Part 1B (Weekly Dosing BMS-986148 Monotherapy Dosing / 28 Day Cycle) Procedural Outline (CA008002)**

Procedure a	Pre-Screening	Screening Visit D-28 to D-1	C1D1	C1D2	C1D4 b	C1D8	C1D15	C1D22	Notes
									block must be provided. [REDACTED] Every effort should be made to provide 20 slides (minimum of 10 slides) for mesothelin IHC testing.
Tumor Assessment		X							Baseline must be within approximately 30 days of C1D1.
Tumor Markers (CA125 and CA19-9)			X						At the time of tumor assessments: serum CA125 for ovarian cancer and mesothelioma subjects only, serum CA19-9 for pancreatic cancer subjects only. Baseline sample collection pre-dose on C1D1.
Concomitant Treatments			X	X	X	X	X	X	
Adverse Event Reporting									
Clinical Complaints		X							Clinical complaints related to the disease under study must be collected within 14 days of the first dose of study drug.
Monitor for Non-SAEs			X	X	X	X	X	X	Non-SAEs will be collected starting with the first dose of study medication and through 60 days after discontinuation of dosing.
Monitor for SAEs		X	X	X	X	X	X	X	All SAEs must be collected from the date of subject's written consent until

**Table 5.1-4: Screening and Cycle 1, Part 1B (Weekly Dosing BMS-986148 Monotherapy Dosing / 28 Day Cycle) Procedural Outline (CA008002)**

Procedure a	Pre-Screening	Screening Visit D-28 to D-1	C1D1	C1D2	C1D4 b	C1D8	C1D15	C1D22	Notes
									60 days from the last dose of study drug or subject's participation in the study if the last scheduled visit occurs at a later time.

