**Table 5.1-6: Screening and Cycle 1 (Part 3: Nivolumab Combination Arm / 21 Day Cycle) Procedural Outline (CA008002)**

Procedure a	Pre-Screening	Screening Visit D-28 to D-1	C1D1	C1D2	C1D4 b	C1D8	C1D15	Notes
								Hep B surface antigen and Hep C antibody (if Hep C antibody is positive reflex to Hep C RNA) or Hep C RNA will be done at screening. Note: Testing for HIV-1 and HIV-2 must be performed at sites where mandated by local requirements. See Section 5.3.1 Urine - screening only, unless clinically indicated. C1D4: CBC only.
Thyroid Function		X						TSH with reflexive fT3 and fT4.
Troponin T or I		X	X			X	X	During Part 3A only. The same evaluation must be collected throughout the study.
Pregnancy Test		X	X					
PK and Immunogenicity Assessments (See Section 5.5)								
Biomarker Assessments [REDACTED]								
[REDACTED]								
Tumor Sample (or Archival) Part 3B: Required for Eligibility	X Part 3B only	X (Part 3A and if not pre-screened in						For Part 3B, subjects must have tumor mesothelin expression [REDACTED]. No other protocol-specific eligibility procedures/assessment should be conducted

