#### **Serum Chemistry**

AST	Total Protein
ALT	Albumin
TB	Sodium
Direct bilirubin (only if TB is elevated)	Potassium
Alkaline phosphatase	Chloride
Lactate dehydrogenase	Calcium
Creatinine	Phosphorus
Blood urea nitrogen or Urea	Magnesium
Uric acid	
Glucose	Creatine kinase with reflex measurement of isoenzymes if elevated

Troponin I or T at screening and Part 1 and Part 3A cycle 1 only.

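### The troponin row notes in Tables 5.1-2, 5.1-4 and 5.1-6 restrict the screening draw to Part 1 or Part 3A, in conflict with the unrestricted troponin exclusion and with Section 5.3.1

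*Protocol*

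**What the plan says.** Protocol Section 3.3.2, criterion 2(e)(v), lists as an exclusion "Troponin (T or I) > the institutional upper limit of normal (ULN"), with no limit by study part. Section 1.5.1 says the same in the risk discussion: subjects with "elevated Troponin I or T will be excluded from the study". Section 3.3 states that "the subject MUST fulfill the required eligibility criteria prior to dosing on Day 1" and allows no exceptions.

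Table 5.1-1 assigns a schedule to each part. Part 2 uses Table 5.1-2 (Q3W) or Table 5.1-4 (QW) for screening and Cycle 1; Parts 3A and 3B both use Table 5.1-6. Each of these tables has a troponin row with an X under Screening and further Xs in Cycle 1. The notes to those rows read:

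- Table 5.1-2: "During Part 1 only. The same evaluation must be collected throughout the study"
- Table 5.1-4: "For Part 1 only. The same evaluation must be collected throughout the study"
- Table 5.1-6: "During Part 3A only. The same evaluation must be collected throughout the study"

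Section 5.3.1, under Serum Chemistry, says: "Troponin I or T at screening and Part 1 and Part 3A cycle 1 only". Section 5.3 says: "Troponin T or I will be monitored QW during the first cycle", without naming a part.

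**The concern.** An exclusion that rests on a laboratory value works only if the value is obtained before dosing. Two of the parts governed by this exclusion, Part 2 and Part 3B, use schedule tables whose troponin note names a different part. Section 5.3 refers the reader to Tables 5.1-2 through 5.1-8 for the required tests, so sites can be expected to work from those tables. A coordinator preparing a Part 2 screening visit who reads the troponin row and its note would reasonably conclude that no draw is needed.

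At stake is who may be dosed. If the draw is omitted, an ineligible subject can enter treatment unnoticed, and there is no baseline value if troponin is measured later for clinical reasons. The programmable eligibility deviations listed in SAP Section 7.2.3 do not include troponin, so that listing would not show the omission. The SAP does provide for non-programmable deviations to be reported elsewhere.

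**Working it through.** **1. Side-by-side reading.**

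| Place | Screening troponin | Cycle 1 troponin |
|---|---|---|
| Exclusion 2(e)(v); Section 1.5.1 | Needed in every part to apply the criterion | Not addressed |
| Tables 5.1-2 and 5.1-4, troponin row | X, under a note limited to Part 1 | Xs, under the same note |
| Table 5.1-6, troponin row | X, under a note limited to Part 3A | Xs, under the same note |
| Section 5.3.1 | Listed, no part named | Part 1 and Part 3A |
| Section 5.3 | Not addressed | Weekly, no part named |

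**2. Does the note reach the screening X?** On its wording, yes.

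- The note applies to the row and names no column.
- Table 5.1-2 serves Parts 1A and 2 together, so the X alone does not show which part it is for; only the note does.
- Where the authors wanted a restriction on one column of Table 5.1-2, they put it in the cell. The Tumor Sample row does this for its pre-screening and screening entries. The troponin cells carry no such text.
- The note's second sentence, on collecting the same evaluation throughout, appears to concern keeping to one assay (T or I). It does not widen the set of parts.

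**3. Is the exclusion itself meant for all parts?** It has no limit, and the same list does state one where it is intended: the autoimmune disease criterion, 2(i), is marked as applying to Part 3 only.

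**4. What does Section 5.3.1 mean?** The natural reading is screening for everyone, plus Cycle 1 draws in Parts 1 and 3A only. It is the only reading that fits the unrestricted exclusion. The sentence is terse, though. It ends in a limiting word and names the same parts as the table notes, so a reader could stretch the limit to screening as well.

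**5. How many subjects are in the parts concerned?** Inputs are from the Synopsis (Number of Subjects) and Section 8.1.

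- Part 1: 30 + 24 = 54. Part 2: 125 to 150. Part 3A: 12. Part 3B: 125 to 150.
- The plan's own totals reproduce. Monotherapy: 54 + 125 = 179 and 54 + 150 = 204. Combination: 12 + 125 = 137 and 12 + 150 = 162.
- All subjects: 179 + 137 = 316 and 204 + 162 = 366.
- Part 2 plus Part 3B: 125 + 125 = 250 and 150 + 150 = 300.
- Share: 250/316 = 79.1% and 300/366 = 82.0%. The other 66 subjects (54 + 12) are in Parts 1 and 3A, where the notes do order the test.

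**6. Cycle 1.** The table notes and Section 5.3.1 agree: Part 1 and Part 3A. The sentence in Section 5.3 is broader. This is a separate inconsistency and does not concern eligibility.

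**The case against.** The strongest reply is that the protocol already gives a route to the test. The Laboratory Tests row in each of the three tables is marked at Screening, has no part restriction and refers to Section 5.3.1, which lists screening troponin. Each table also has an unrestricted Inclusion/Exclusion Criteria row at Screening, and Section 3.3 requires every criterion to be met before dosing. A site that follows these has to establish troponin status whatever the row note says.

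This reply stands in part. A reader might infer that the exclusion cannot be applied in Parts 2 and 3B. The documents do not support that, because the route through Section 5.3.1 and the exclusion list exists. The reply does not remove the conflict. Troponin has its own row with its own note, the pointer to Section 5.3.1 sits in a different row, and the sentence it leads to is itself open to misreading.

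Two further inferences should also be set aside:

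- **Damage to the primary endpoint.** Laboratory grade shift from baseline needs post-baseline values. On the table notes, Parts 2 and 3B have no scheduled on-treatment troponin, and the SAP laboratory sections name no troponin analysis. Table 4.5.2-1 lists troponin actions under a heading covering Parts 1, 2 and 3, but it says what to do when an elevation is found and does not schedule testing.
- **All Part 2 and Part 3B subjects affected.** That would assume every site ignores both Section 5.3.1 and the exclusion list.

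Other cardiac checks (MUGA or echocardiogram and ECG at screening, echocardiograms on treatment) are scheduled in every part, so cardiac screening does not rest on troponin alone.

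**Conclusion.** The inconsistency is real and should be corrected. Read literally, the notes in Tables 5.1-2, 5.1-4 and 5.1-6 remove the screening troponin from Parts 2 and 3B, while exclusion 2(e)(v), Section 1.5.1 and the natural reading of Section 5.3.1 require it. The consequence is conditional: a site relying on the troponin row alone could omit the test behind an exclusion criterion and dose a subject who should have been excluded.

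The parts exposed to the conflicting instruction hold 79% to 82% of planned subjects, assuming enrollment at the Synopsis figures. How many would actually be dosed in error cannot be estimated. The documents give neither the frequency of elevated troponin at screening nor any indication of how sites read the note.

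The unrestricted Cycle 1 sentence in Section 5.3 is a second, smaller mismatch. No view is taken here on which on-treatment troponin schedule is right.

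**What to change.** Reconcile the three table notes with exclusion 2(e)(v) and Section 5.3.1, so that the schedule for each part orders every test on which that part's eligibility criteria rest. One way is to attach the part restriction to the Cycle 1 columns only, leaving the screening X unrestricted, and to split the Section 5.3.1 sentence so that screening and Cycle 1 are stated separately. Separately, reconcile the Cycle 1 sentence in Section 5.3 with the tables and Section 5.3.1; which on-treatment schedule stands is for the sponsor to decide.

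The cost is wording in three table notes and two sentences at the next amendment. No test is added beyond what the exclusion already implies. At any site that has been omitting it, the extra work is one troponin measurement at a screening visit where laboratory tests are already scheduled.
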